12.4. Final Analysis

The final analysis will be conducted when all patients with stage 1 to 3c disease have completed 1 year of study treatment or have met other specified withdrawal criteria and patients with mBC have completed study treatment, discontinued treatment or met other specified withdrawal criterion.

12.5. Determination of Sample Size

Based on feasibility, 3-5 patients are to be enrolled in this study.

13. SAFETY DATA COLLECTION, RECORDING, AND REPORTING

All observed or volunteered AEs regardless of treatment group or causal relationship to investigational product will be recorded on the AE page(s) of the CRF.

13.1. Definitions

13.1.1. Adverse Events

An AE is any untoward medical occurrence in a patient or clinical investigation patient administered a pharmaceutical product, and which does not necessarily have a causal relationship with the treatment. An AE can therefore be any unfavorable and unintended sign (including abnormal laboratory finding), symptom, or disease temporally associated with the use of an investigational product, whether or not considered related to the medicinal product (definition per International Conference on Harmonisation [ICH] E2A and E6 R1).

All AEs, regardless of seriousness, severity, or presumed relationship to study therapy, must be recorded using medical terminology on the AE CRF page. Whenever possible, diagnoses should be given when signs and symptoms are due to a common etiology (eg, cough, runny nose, sneezing, sore throat, and head congestion should be reported as “upper respiratory infection”). All measures required for AE management must be recorded in the source document and reported according to Sponsor instructions.

For all AEs, the Investigator must pursue and obtain information adequate to both determine the outcome of the AE and to assess whether it meets the criteria for classification as a SAE (see [Section 13.3](#) on SAEs) requiring immediate notification to the Sponsor or its designated representative. For all AEs, sufficient information should be obtained by the Investigator to determine the causality of the AE.

Interventions for pretreatment conditions (eg, elective cosmetic surgery) or medical procedures that were planned before study enrollment are not considered AE.

13.1.2. Abnormal Laboratory Results

The criteria for determining whether an abnormal laboratory test result should be reported as an AE are as follows:

- Test result is associated with accompanying symptoms, and/or,
- Test result requires additional diagnostic testing or medical/surgical intervention (merely repeating an abnormal test, in the absence of any of the above conditions, does not meet criteria for reporting an AE), and/or
- Test result leads to a change in study dosing or discontinuation from the study, significant additional concomitant drug treatment or other therapy, and/or
- Test result leads to any of the outcomes included in the definition of a SAE, and/or
- Test result is considered to be an AE by the Investigator or by the Sponsor

Any abnormal test result that is determined to be an error does not require reporting as an AE, even if it did meet one of the above criteria except for when the test result leads to any of the outcomes included in the definition of a SAE. Clinically significant laboratory results must be recorded in the patient's CRF.

13.1.3. Serious Adverse Events

An SAE is defined as any untoward medical occurrence that at any dose (ICH E2A and E6 R2):

- Results in death
- Is life-threatening
This means that the patient is at risk of death at the time of the event; it does not mean that the event hypothetically might have caused death if it were more severe.
- Requires inpatient hospitalization or prolongation of existing hospitalization
- Results in persistent or significant disability or incapacity
- Is a congenital anomaly or birth defect

Medical and scientific judgment should be exercised in deciding whether expedited reporting is appropriate in other situations, such as important medical event(s) that may not be immediately life-threatening or result in death or hospitalization but that may jeopardize the patient or require intervention to prevent one of the other outcomes listed in the definition above. These should also usually be considered serious. Examples of such events are intensive treatment in an emergency room or at home for allergic bronchospasm; blood dyscrasias or convulsions that do not result in hospitalization; or development of drug dependency or drug abuse.

Disease progression should not be recorded as an AE or SAE term; instead, signs and symptoms of clinical sequelae resulting from disease progression will be reported if they fulfill the SAE definition.

13.1.4. Hospitalization

Any inpatient hospital admission that includes a minimum of an overnight stay to a healthcare facility meets the criteria for 'hospitalization'. Admission also includes transfer within the hospital to an acute/intensive care unit (eg, from the psychiatric wing to a medical floor, medical floor to a coronary care unit, neurological floor to a tuberculosis unit).

The following are not considered to be hospitalization:

- Rehabilitation facilities
- Hospice facilities
- Respite care (eg, caregiver relief)
- Skilled nursing facilities
- Nursing homes
- Routine emergency room admissions
- Same day surgeries (as outpatient /same day/ambulatory procedures)

Hospitalization or prolongation of hospitalization in the absence of a precipitating, clinical AE is not in itself a SAE. Examples include:

- Admission for treatment of a preexisting condition not associated with the development of a new AE or with a worsening of the preexisting condition (eg, for work-up of persistent pre-treatment lab abnormality)
- Social admission (eg, patient has no place to sleep)
- Administrative admission (eg, for yearly physical examination)
- Protocol-specified admission during a study (eg, for a procedure required by the study protocol)
- Optional admission not associated with a precipitating clinical AE (eg, for elective cosmetic surgery)
- Hospitalization for observation without a medical AE
- Pre-planned treatments or surgical procedures should be noted in the baseline documentation and/or for the individual patient
- Admission exclusively for the administration of blood products

Diagnostic and therapeutic non-invasive and invasive procedures, such as surgery, should not be reported as AEs. However, the medical condition for which the procedure was performed should be reported if it meets the definition of an AE. For example, an acute appendicitis that begins during the AE reporting period should be reported as the AE, and the resulting appendectomy should be recorded as treatment of the AE.

13.1.5. Suspected Unexpected Serious Adverse Reaction

Suspected unexpected serious adverse reactions (SUSAR) are events which are serious as per the above criteria, the nature or severity of which is not consistent with the applicable product information (eg, **IB**) and are judged by the Investigator or by the Sponsor to be related to investigational product. For a non-Sponsored investigational product (eg, a comparator product) with a marketing authorization, the expectedness of an AE will be determined by whether or not it is listed in the package insert/SmPC.

13.1.6. Severity Assessment

Adverse events will be graded by the Investigator according to the NCI CTCAE v.4.0 (Publish Date: May 28, 2009, <http://ctep.cancer.gov/reporting/ctc.html>), according to the following general categories:

Grade 1: Mild; asymptomatic or mild symptoms; clinical or diagnostic observations only; intervention not indicated.

Grade 2: Moderate; minimal, local or noninvasive intervention indicated; limiting age-appropriate instrumental activities of daily living.

Grade 3: Severe or medically significant but not immediately life-threatening; hospitalization or prolongation of hospitalization indicated; disabling; limiting self-care activities of daily living.

Grade 4: Life-threatening consequences; urgent intervention indicated.

Grade 5: Death related to AE.

Note the distinction between the severity and the seriousness of an AE. A severe event is not necessarily a serious adverse event. For example, a headache may be severe (interferes significantly with patient's usual function) but would not be classified as serious unless it meets one of the criteria for SAEs, listed above.

13.1.7. Causality Assessment

The Investigator's assessment of causality must be provided for all AEs (serious and non-serious); the Investigator must record the causal relationship in the CRF and report such an assessment in accordance with the serious adverse reporting requirements, if applicable.

A suspected adverse reaction means any AE for which there is a reasonable possibility that the investigational product caused the AE. An Investigator's causality assessment is the determination of whether there exists a reasonable possibility that the investigational product caused or contributed to an AE; generally the facts (evidence) or arguments to suggest a causal relationship should be provided. If the Investigator does not know whether or not the investigational product caused the event, then the event will be handled as "related to investigational product" for reporting purposes, as defined by the Sponsor (see [Section 13.2](#)). If the Investigator's causality assessment is "unknown but not related to investigational product", this should be clearly documented on study records.

For all AEs, sufficient information should be obtained by the Investigator to determine the causality of the AE (eg, investigational product or other illness). The relationship of the AE to the study treatment (investigational product, comparator or placebo [as applicable]) will be assessed following the definitions below:

- 'No' (unrelated): Any event that does not follow a reasonable temporal sequence from administration of investigational product AND is likely to have been produced by the patient's clinical state or other modes of therapy administered to the patient.
- 'Yes' (related): Any reaction that follows a reasonable temporal sequence from administration of investigational product AND follows a known response pattern to the suspected investigational product AND recurs with re-challenge, AND/OR is improved by stopping the investigational product or reducing the dose.

In addition, if the Investigator determines an AE is associated with study procedures, the Investigator must record this causal relationship on the AE CRF page and report such an assessment in accordance with the SAE reporting requirements, if applicable.

13.1.8. Special Reporting Situations

Safety events of interest on the Sponsor's investigational product that may require expedited reporting and/or safety evaluation include, but are not limited to:

- Overdose of an investigational product
- Suspected abuse/misuse of an investigational product
- Inadvertent or accidental exposure to an investigational product
- Medication error that may result from the administration or consumption of the wrong drug, by the wrong patient, at the wrong time, or at the wrong dosage strength
- Suspected transmission via an investigational product of an infectious agent

Special reporting situations should be recorded on the AE CRF page. Any special reporting situation that meets the criteria of a SAE should be recorded on the SAE form and reported as required (see [Section 13.3](#)).

13.2. Reporting Adverse Events

For serious and non-serious AEs, the reporting period to the Sponsor (or its designated representative) begins from the time that the patient provides informed consent, which is obtained prior to the patient's participation in the study, i.e., prior to undergoing any study-related procedure and/or receiving investigational product, through 28 calendar days after the last administration of the investigational product.

For all AEs with causal relationship to the investigational product, follow-up by the Investigator may be required until the event or its sequelae resolve or stabilize at the level acceptable to the Investigator, and the Sponsor concurs with that assessment.

If a patient begins a new anticancer therapy, the AE reporting period for non-serious AEs ends at the time the new treatment is started. Death must be reported if it occurs during the SAE reporting period after the last dose of investigational product, irrespective of any intervening treatment.

The Sponsor will evaluate any safety information that is spontaneously reported by an Investigator beyond the time frame specified in the protocol.

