4.2. Study Duration and Termination of Study

The approximate duration of the study is 1.5 years.

Patients with stage 1 to 3c disease receiving extended adjuvant therapy are anticipated to participate in the study for approximately 1 year. This includes 1 month for screening, approximately 12 months for the active treatment phase until progression of disease or intolerance to study prescribed therapy, and safety follow-up visit 28 days after the last dose of neratinib.

Patients with mBC are anticipated to participate in the study for an average of 12 months. This includes approximately 1 month for screening, an estimated average of 9.5 months for the active treatment phase, and an estimated average of 1 month for initial Safety Follow-up. Patients who permanently discontinue treatment due to unacceptable toxicity will be followed-up for 28 days after the last dose of neratinib to collect any adverse events (AEs) ([Section 9.4](#)).

The primary analysis will be conducted after all patients have completed two sets of colon biopsies. The final analysis will be conducted when all patients with stage 1 to 3c breast cancer have completed 1 year of study treatment or have met other specified withdrawal criteria and patients with mBC have discontinued therapy or have met other specified withdrawal criteria (see [Section 10](#)).

The study will end when all patients have been followed up for 28 days after the last dose of neratinib.

In the event that end of treatment (EOT) is declared earlier by the Sponsor, patients will be offered the opportunity to complete treatment through a treatment extension study.

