8.2. Safety Assessments

8.2.1. Safety Endpoints

- The primary endpoint is descriptive assessment of colon pathology during the first 28 days of neratinib therapy.
- The secondary endpoint is the incidence and severity of diarrhea during the first 28-day cycle.

The incidence of TEAEs and SAEs for Cycle 1 through 28 days of neratinib monotherapy following the second study colonoscopy procedure in patients with stage 1 to 3c breast cancer treated in the extended adjuvant setting, and in Cycle 2 in patients with mBC will also be reported. AEs and SAEs will be graded according to the National Cancer Institute Common Terminology Criteria (NCI CTCAE), version 4.0 or higher.

After the completion of 28 days following the second study colonoscopy procedure in patients with stage 1 to 3c breast cancer treated in the extended adjuvant setting and in Cycle 2 in patients with mBC through 28 calendar days after the last administration of neratinib, only SAE data will be collected and summarized. SAEs will be followed until resolution or until condition stabilizes. Should an Investigator be made aware of any SAEs occurring any time after the reporting period that may be causally related to administration of neratinib, it should be promptly reported. All SAEs must be reported within 24 hours of awareness of the event using the SAE Report Form. More details on AEs can be found in Section 13.

SAEs will be followed until resolution or until condition stabilizes. Should an Investigator be made aware of any SAEs occurring any time after the reporting period that may be causally related to administration of neratinib, it should be promptly reported. All SAEs must be reported within 24 hours of awareness of the event using the SAE Report Form. More details on AEs can be found in Section 13.

Safety will also be assessed based on medical history, vital sign measurements, physical examination findings, and laboratory assessments. Refer to the Schedule of Procedures (Appendix 1) for time points.

The diary used for recording of investigational product intake will also be used by patients to document any other study treatment. In case of diarrhea, it also serves to document the number of loose stools per day, and use of loperamide/other antidiarrheal treatments taken.

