9.4. Safety Follow-up Visit

Patients who complete the active treatment phase or who discontinue due to unacceptable toxicity will be followed-up for 28 days after the last dose of neratinib to collect SAEs.

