10. PATIENT WITHDRAWAL AND REPLACEMENT

10.1. Investigational Product Discontinuation

Patients **must** be discontinued from **investigational product** under the following circumstances listed below and in [Appendix 2](#), unless otherwise agreed with the Medical Monitor:

- If the patient requires more than 2 dose reductions of neratinib (see [Appendix 2](#))
- If neratinib is withheld due to an SAEs for >28 days. Patients who are clinically benefiting from therapy with neratinib may be resumed on therapy after 28 days if approved in advance by the Sponsor
- Disease recurrence
- Initiation of alternative anti-cancer therapy. Any concurrent chemotherapy, radiotherapy (including palliative radiotherapy), surgery related to cancer, anticancer immunotherapy, or other anticancer treatments including other investigational agents (see [Section 7.3](#)).
- Pregnancy (see [Section 13.4](#))
- Investigator request
- Patient request (i.e., withdrawal of consent for treatment)
- AEs/toxicity

Withdrawal due to AE should be distinguished from withdrawal due to other causes, and recorded on the appropriate AE page of CRF. If a patient withdraws due to toxicity, even if discontinuation is not otherwise required per protocol guidelines, the withdrawal should be classified as withdrawal due to AE.

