3. DEFINITIONS

Baseline

The baseline value for a parameter of interest is the last measurement obtained prior to or on the date of the first dose of neratinib.

Cycle

The first cycle is 28 days for all subjects, all of whom receive neratinib and loperamide prophylaxis. After the first 28-day cycle, stage 1 to 3c breast cancer patients receiving extended adjuvant treatment return to clinic every 3 months. Metastatic breast cancer patients return to clinic at scheduled 21-day cycles, during with time they receive both neratinib and capecitabine.

Study Day 1

Study Day 1 is the date the first dose of neratinib is taken.

Treatment duration

Treatment duration in days = last dose date - first dose date + 1

Actual Dose Intensity

The actual dose intensity is defined as the cumulative actual dose divided by treatment duration.

Relative Actual Dose Intensity

The relative actual dose intensity is defined as the actual dose intensity divided by the planned dose intensity.

Prescribed Dose Intensity

The prescribed dose intensity is defined as the cumulative prescribed dose divided by treatment duration.

Treatment-Emergent Adverse Event (TEAE)

A TEAE is defined as an AE that occurs or worsens on or after the first administration of neratinib and up to 28 days after the second colonoscopy in patients with stage 1 to 3c breast cancer, and following completion of Cycle 2 in mBC patients.

Investigational Product (IP)

Investigational product (IP) is used to reference neratinib and capecitabine.

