6.7 Study Medications

6.7.1 Study Medication (Neratinib)

Exposure to neratinib during the study will be listed. Variables will include treatment duration in months, cumulative actual dose (mg), actual dose intensity (mg/day), relative actual dose intensity, cumulative prescribed dose, prescribed dose intensity, and compliance. The compliance for neratinib is calculated by using actual dose intensity divided by the prescribed dose intensity.

Indicator for dose reduction (yes/no), dose reduction due to AE (yes/no), and the lowest dose reduction level, will be included in the listing. In addition, indicator for the dose withheld due to AE (yes/no) will be included.

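### Protocol 13.2 collects non-serious adverse events to 28 days after the last dose; other sections and the SAP stop at about Day 55-61 (stage 1-3c) or Day 48-55 (mBC)

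*Protocol*

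**What the plan says.** **Longer rule.** Protocol 13.2: "For serious and non-serious AEs, the reporting period to the Sponsor (or its designated representative) begins from the time that the patient provides informed consent", and it runs "through 28 calendar days after the last administration of the investigational product". The only earlier end it gives for non-serious events is the start of a new anticancer therapy. The opening of Section 13 asks for all AEs on the CRF and sets no cut-off. Section 4.2 says that patients stopping for toxicity are "followed-up for 28 days after the last dose of neratinib to collect any adverse events (AEs"), citing 9.4; SAP 2.3.1 repeats this.

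**Shorter rule.** Protocol 8.2.1 collects all AEs for an early period only. That period ends 28 days after the second colonoscopy in stage 1-3c patients and with Cycle 2 in mBC patients. From then "through 28 calendar days after the last administration of neratinib, only SAE data will be collected and summarized". The synopsis, 12.3 and the Appendix 1 footnotes say the same. Section 9.4, the section that 4.2 cites, says patients "will be followed-up for 28 days after the last dose of neratinib to collect SAEs". SAP 3 defines a TEAE as running "up to 28 days after the second colonoscopy in patients with stage 1 to 3c breast cancer", and to completion of Cycle 2 in mBC.

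**Records with no stated time limit.** Protocol 10.1 wants a withdrawal due to an AE "recorded on the appropriate AE page of CRF". Protocol 10.3 requires the reasons for discontinuation on the CRF in all cases, and SAP 6.1 lists them. SAP 6.7.1 adds, for neratinib: "Indicator for dose reduction (yes/no), dose reduction due to AE (yes/no), and the lowest dose reduction level, will be included in the listing". It also flags doses withheld for an AE, and SAP 6.7.2 has the same flags for capecitabine.

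**The concern.** The two rules give different answers to one practical question: does a site enter a non-serious AE that begins in month 4? Section 13.2 says yes and 8.2.1 says no. With 3-5 patients at about two sites, one patient handled under the other rule visibly changes the safety tables.

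The shorter rule also sits badly with the rest of the plan. Appendix 2 triggers holds, reductions and stops from Grade 2 and Grade 3 events, which need not be serious. After the early period, such an event would set the SAP 6.7 dose-change flag with no matching AE behind it. It would also be missing from the incidence tables of TEAEs leading to reduction, interruption or discontinuation, and from the listing of TEAEs leading to IP discontinuation.

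**Working it through.** **1. Where each rule ends.** Inputs: second colonoscopy on Day 30 ± 3, so Day 27-33 (Protocol 4.1); one year of adjuvant treatment, taken as 365 days; Cycle 2 of 21 days, starting after the colonoscopy (Table A1.2 footnote a). Table A1.2 footnote o instead puts the mBC colonoscopy on Day 1 of Cycle 2 (+5 days), so Day 29-34. For mBC I take Cycle 2 to start the day after the colonoscopy.

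| Rule | Arithmetic | Non-serious collection ends |
|---|---|---|
| 13.2, full-year adjuvant | 365 + 28 | Day 393 |
| Shorter rule, stage 1-3c | 27 + 28 to 33 + 28 | Day 55-61 |
| Shorter rule, mBC, Day 30 ± 3 | 27 + 21 to 33 + 21 | Day 48-54 |
| Shorter rule, mBC, footnote o | 29 + 21 to 34 + 21 | Day 50-55 |

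For stage 1-3c the gap is 393 - 61 = 332 to 393 - 55 = 338 days. Counted from Day 1, the shorter window is 55/393 = 14.0% to 61/393 = 15.5% of the longer one. Both rules start at consent; with the full 28 days of screening added, the share is 83/421 = 19.7% to 89/421 = 21.1%. For mBC, at the planned average of 9.5 months (about 289 days at 30.44 days a month), the window is 48/289 = 16.6% to 55/289 = 19.0% of treatment.

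**2. Can the texts be read together?**
- Ending non-serious reporting at new anticancer therapy (13.2) has little purpose if that reporting already closed around Day 60.
- Section 8.2.1 states the shorter rule and then sends the reader to Section 13, which holds the longer one.
- Section 4.2 (any AEs) cites 9.4 (SAEs) for the same 28 days.

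They cannot.

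**3. What the SAP does with late events.** TEAEs end with the shorter window. A serious or fatal event on Day 200 is therefore outside the serious and fatal TEAE tables of SAP 6.9.2. It appears only in the SAE and death listings, although Protocol 12.3 says late SAEs will be summarized and SAP 8 declares no change from the protocol. A stage 1-3c patient with no second colonoscopy is replaced (Protocol 10.4) but stays in the safety population (SAP 5.1), and the TEAE window then has no end date.

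**4. How many stops could be affected.** Only diarrhea has figures. In Study 3004, 237/1408 = 16.8% stopped for diarrhea; serious diarrhea was 1.6%, and 0.016 × 1408 is about 23. At most 23/237 = 9.7% of those stops were serious, so at least 90% were not. Their timing is not given. If a fraction f of stops came after the early window, and all 23 serious cases were among them, the non-serious share of late stops is at least 1 - 23/(237f):

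| f (assumed) | Minimum non-serious share |
|---|---|
| 20% | 51% |
| 40% | 76% |
| 80% | 88% |

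It falls below half when f is under about 19%.

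For this study, 3 × 0.168 = 0.5 to 5 × 0.204 = 1.0 diarrhea stops are expected in total, using Study 3004 and Study 6201 (28/137 = 20.4%). The chance of at least one is 42-68%. If 20-83% were late (83% is 304/365, stops spread evenly over the year), 0.1-0.85 late diarrhea stops are expected.

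**The case against.** The best defence is that SAE-only late collection is deliberate. It is stated repeatedly, SAP 3 follows it, and 12.3 limits its listing of AEs resulting in discontinuation to the early period. Section 13 reads as template text, with references to treatment group, comparator and placebo. Neratinib is already approved in the extended adjuvant setting, and this is a small descriptive study presented mainly through listings and narratives. That supports the shorter rule as a legitimate choice. It does not tell a site to disregard 13.2 and 4.2.

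A reader might go further and infer that most late toxicity stops would never reach the safety data. The documents do not support that. The stop and its reason are recorded and listed without a time limit (Protocol 10.1 and 10.3, SAP 6.1), and SAEs and deaths have their own listings. What is lost is the event's term, grade and dates in the TEAE outputs. Nor does 'most' follow: the figures cover diarrhea only and give no timing of stops, Grade 3 diarrhea is concentrated in the first month, and an overall non-serious share of 90% does not carry over to the late subset. Study 3004 also had no mandated prophylaxis, whereas loperamide is mandatory here.

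Two side points are minor. Table A1.1 has two footnotes marked r. The first gives the colonoscopy-based window correctly for stage 1-3c, so 'Cycle 2' in the second is leftover wording. Section 9.4 names only completers and toxicity stops, but 4.1 and 9.6 apply the 28-day follow-up to all patients.

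**Conclusion.** The contradiction stands. A site cannot comply with both 13.2 and 8.2.1, and for a full-year stage 1-3c patient they differ by about 332-338 days of non-serious AE collection. Under the shorter rule, late AEs behind a dose change are missing from the TEAE outputs while the dose-change flags remain. Under either rule, late SAEs fall outside the serious and fatal TEAE tables.

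The day counts assume 365 days of treatment and the scheduled colonoscopy windows. The number of late stops affected is unknown; the 0.1-0.85 range covers diarrhea only and rests on an assumed timing. The primary endpoint and the Cycle 1 diarrhea and marker endpoints fall inside both windows, and SAEs are to be collected to 28 days after the last dose under both rules. This should be fixed, but it does not threaten the study's main results.

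**What to change.** - State one AE collection window and use it in the synopsis, Protocol 4.2, 8.2.1, 9.4, 12.3, 13.2, Appendix 1 and SAP 3.
- If the SAE-only late period is kept, amend 13.2 and 4.2 to match. Add that any AE leading to a hold, reduction or discontinuation of neratinib or capecitabine is recorded through 28 days after the last dose, as Protocol 10.1 and SAP 6.7 already imply.
- In SAP 3 and 6.9.2, report SAEs, deaths and those AEs through 28 days after the last dose. Give the TEAE window an end date for patients with no second colonoscopy.
- In the Table A1.1 footnotes, replace the leftover 'Cycle 2' and 'Cycle 3' wording with 28 days after colonoscopy 2.
- Align 9.4 with 9.6 so that follow-up covers every dosed patient.

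The cost is protocol and SAP wording plus a few extra AE entries in a 3-5 patient study.
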